9.2.6 Important Protocol Deviations

An important protocol deviation (IPD) is a deviation that may significantly affect the completeness, accuracy, or reliability of the study data or that may significantly affect a subject's rights, safety, or well-being. IPD rules will be developed and finalized before database lock.

IPDs will be identified by the PD review team according to PD plan.

IPDs will be provided in an individual subject data listing.

9.3 Efficacy Analysis

9.3.1 Spirometry (Part D Only)

The spirometry parameters: FEV₁ (L), forced vital capacity (FVC) (L), FEV₁/FVC (ratio), and forced expiratory flow, midexpiratory phase (FEF_{25%-75%}) (L/s) and their corresponding percent predicted values (percentage point) and change from baseline will be summarized by treatment group using descriptive statistics for the FAS. Percent predicted FEV₁ is the ratio of FEV₁ (L) and predicted FEV₁ (L), expressed as a percentage. See [Appendix B](#) for more details.

In addition, a mixed-effects model for repeated measures (MMRM) with change from baseline at Day 15 and Week 4 predose for percent predicted forced expiratory volume in 1 second (ppFEV₁) as the dependent variable will be performed for the FAS. The model will include treatment group, visit, and treatment-by-visit interaction as fixed effects. The model will be estimated using restricted maximum likelihood. Denominator degrees of freedom for the *F* test for fixed effects will be estimated using the Kenward-Roger approximation. A compound symmetry covariance structure will be used to model the within-subject errors. Conditional on the fixed effects, missing data due to treatment or study discontinuation will be assumed to be missing at random.

The adjusted means and 2-sided 95% CIs of the treatment effect through Day 29 (averaged over Day 15 and 29), with corresponding *P* values for all within-group comparisons, will be estimated using MMRM.

In addition, the adjusted mean and 95% CI of the within-treatment difference at each post-baseline visit through Day 29 for each treatment group will be provided along with the *p*-value.

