- **TE Period 2 (tablet [fed])** will begin from administration of VX-121 tablet in the fed state (1) until the administration of VX-121 tablet in the fed state and with milk, or (2) the Safety Follow-up Visit for subjects who do not have the dose of VX-121 tablet in the fed state and with milk and have a Safety Follow-up Visit, or (3) 7 days after the last dose of study drug for subjects who do not have the dose of VX-121 tablet in the fed state and with milk, and do not have a Safety Follow-up Visit.
- **TE Period 3 (tablet [fed and with milk])** will begin from the administration of VX-121 tablet in fed state and with milk through the Safety Follow-up Visit or 7 days after the last dose of study drug for subjects who do not have a Safety Follow-up Visit..

For subjects participating in Part D, the **TE Period** will be from first dose date of study drug to Safety Follow-up Visit for subjects who have a safety follow-up visit; or 28 days after the last dose date of study drug for subjects who do not have a safety follow-up visit.

Treatment Groups

The Treatment Groups in Part A (excluding Cohorts A3 and A9), B, C and D will be defined as the corresponding VX-121 dose groups.

The 2 Treatment Groups in Cohort A3 will correspond to suspension [fed] and suspension [fed and with milk] respectively.

The 3 Treatment Groups in Cohort A9 will correspond to suspension [fed], tablet [fed] and tablet [fed and with milk] respectively.

Baseline value

The baseline value will be defined as the most recent non-missing measurement (scheduled or unscheduled) collected before the first dose of study drug. If a pre-dose measurement is missing and no drug-free unscheduled assessments are performed before the first dose of the study, the baseline will be missing. For ECG, the baseline value will be defined as the most recent non-missing measurement (or the average of triplicate measurements, if the most recent non-missing measurements are obtained in triplicate), before the first dose of study drug of the Treatment Period.

Absolute change from baseline will be calculated as post-baseline value – baseline value.

Relative change from baseline will be calculated as (post-baseline value – baseline value)/baseline value.

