9.6 Pharmacodynamic Analysis (Part D Only)

The sweat chloride value for a given visit will be calculated as the mean of the non-missing sweat chloride measurements obtained on the left and right arms at that visit. If one of the two arm measurements at a time point is missing, the other will be used as the mean. A volume ≥ 15 μL is required for an accurate determination of sweat chloride. Any results reported as having volume < 15 μL will be considered missing. Any sweat chloride values reported as < 10 mmol/L or > 160 mmol/L will be considered missing.

The analysis of sweat chloride data will be based on the FAS. A summary of raw values and change from baseline values will be provided at each scheduled visit by treatment group and overall using descriptive statistics.

The same MMRM model as for ppFEV₁ will be used to analyze the change from baseline for sweat chloride. Adjusted means and 2-sided 95% CIs of the treatment effect through Day 29 (averaged over Day 15 and 29), with 2-sided *P* values for all within-group comparisons, will be estimated using MMRM.

In addition, a listing containing individual subject data at scheduled and unscheduled visits will be provided.

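### The Part D MMRMs for ppFEV1 and sweat chloride omit the baseline value; with 9 vs 3 subjects, part of a chance baseline difference enters any comparison of the two arms

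*SAP*

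**What the plan says.** SAP 9.3.1 fits an MMRM "with change from baseline at Day 15 and Week 4 predose for percent predicted forced expiratory volume in 1 second" and gives its fixed effects in full: "The model will include treatment group, visit, and treatment-by-visit interaction as fixed effects". Protocol 12.3.3.1 lists the same three terms. SAP 9.6 adds: "The same MMRM model as for ppFEV₁ will be used to analyze the change from baseline for sweat chloride"; protocol 12.4.2 does likewise. The outcome is a change score; SAP 9.1 says: "Absolute change from baseline will be calculated as post-baseline value – baseline value".

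The planned outputs are adjusted means and 95% CIs averaged over Days 15 and 29, with P "values for all within-group comparisons, will be estimated using MMRM". For ppFEV1 the SAP also plans "the adjusted mean and 95% CI of the within-treatment difference at each post-baseline visit through Day 29 for each treatment group". It calls the averaged quantity a treatment effect but defines no TC-minus-placebo contrast.

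Protocol Table 3-7 schedules spirometry and sweat chloride at screening and on Day 1, so a baseline should exist for every subject. Figure 9-1 of the protocol shows 9 active and 3 placebo subjects. Protocol 9.2 and SAP 7.4 name no stratification factor for Part D. No baseline-adjusted analysis is planned, even as a sensitivity analysis.

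**The concern.** Protocol 9.3.1 justifies the placebo arm as the means of judging whether observed changes come from treatment or from study conditions. Readers will therefore set the two arms' mean changes side by side, although the SAP specifies no contrast. When baseline and post-baseline values are imperfectly correlated, subjects with low baselines tend to rise and those with high baselines tend to fall. Subtracting baseline does not remove this regression to the mean. A mean of 3 placebo subjects depends noticeably on which baselines were drawn, and with no stratification named, the model is the only place to deal with it. With complete data, the adjusted means of the present model are simply the raw mean changes. If nothing is fixed in advance, any adjustment would be chosen after the placebo baselines are known.

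**Working it through.** The plan states no power, SD or effect size (SAP 7.3), so there is no figure of its own to reproduce beyond 12 × 3/4 = 9 and 12 × 1/4 = 3, which agree with protocol Figure 9-1.

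**Assumptions.** Equal variance and a common correlation r among baseline, Day 15 and Day 29; complete data. The documents give neither r nor an SD, so r is varied. With complete data, the compound-symmetry MMRM averaged over two visits reduces to a two-sample analysis of each subject's mean change (10 df). Adding baseline makes it an ANCOVA (9 df).

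**1. Likely size of the imbalance.** SD of the baseline difference = sqrt(1/9 + 1/3) = 0.667 baseline SD. For normal baselines, P(|difference| > 0.5 SD) = P(|Z| > 0.75) = 45%, and P(|difference| > 1 SD) = P(|Z| > 1.5) = 13%.

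**2. How much enters the results.** The slope of change on baseline is -(1 - r). If the active baseline mean exceeds the placebo mean by D, the active arm lies (3/12)D = 0.25D above the overall mean and the placebo arm (9/12)D = 0.75D below it. So:

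- active mean change shifts by -0.25(1 - r)D;
- placebo mean change shifts by +0.75(1 - r)D;
- the TC-minus-placebo difference shifts by -(1 - r)D.

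With baseline in the model, the shift in the difference is zero. Simulation (100,000 trials per r) reproduced these slopes.

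**3. Precision of the arm difference.** Variance ratio, adjusted to unadjusted = (1 + 2r)/3 × (1 + 1/(12 - 4)) = 1.125(1 + 2r)/3. The variances are equal at r = (3/1.125 - 1)/2 = 0.83. Allowing for the t quantiles, (2.262/2.228)² = 1.031, CI widths are equal at r = (3/(1.125 × 1.031) - 1)/2 = 0.79.

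Shifts are absolute sizes in baseline SDs per 1 SD of imbalance. Half-widths are simulated mean 95% CI half-widths for the arm difference, also in SDs.

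| r | Shift in difference | Placebo mean | Active mean | Half-width, unadjusted | Half-width, adjusted | Ratio |
|---|---|---|---|---|---|---|
| 0.5 | 0.50 | 0.375 | 0.125 | 1.253 | 1.095 | 0.87 |
| 0.7 | 0.30 | 0.225 | 0.075 | 0.972 | 0.930 | 0.96 |
| 0.8 | 0.20 | 0.150 | 0.050 | 0.793 | 0.791 | 1.00 |
| 0.9 | 0.10 | 0.075 | 0.025 | 0.561 | 0.580 | 1.03 |
| 0.95 | 0.05 | 0.038 | 0.013 | 0.397 | 0.417 | 1.05 |

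**4. In ppFEV1 points (illustration only).** Assume an SD of 10 to 14.4 points; the upper value is that of a uniform spread over the 40 to 90 entry range, 50/sqrt(12). A typical imbalance of 0.667 SD is then 6.7 to 9.6 points. It shifts the arm difference by 2.0 to 2.9 points at r = 0.7 and by 0.7 to 1.0 at r = 0.9.

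**5. Behaviour over repeated randomizations.** In the same simulations, the type I error of an arm comparison is close to 5% with and without the covariate.

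**6. Within-group CIs from the adjusted model.** Evaluated at the overall baseline mean, the adjusted model's CI for the active arm covers about 92% at r = 0.5, against 95% from the unadjusted model. The usual standard error treats the observed baseline mean as fixed.

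**The case against.** A reader might infer that a baseline imbalance passes in full into the estimated change, that the planned estimates are biased, or that the planned P values are invalid. The documents support none of these. Baseline is already subtracted, so only (1 - r) remains, with the opposite sign. Randomization makes the unadjusted difference unbiased on average, and its CI already carries the variation due to imbalance: at r = 0.5, a 0.50 SD shift lies well inside a half-width of 1.25 SD. The planned CIs and P values are within-group, so a difference between arms is not a direct input to them, and the active mean moves little.

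It can also be said that these are secondary, early-phase analyses with no decision rule attached. Values and changes are tabulated by arm and every subject is listed, so imbalance will be visible. The covariate may not improve precision either: the required stable disease and regimen, with a wide entry range, make a high r for ppFEV1 plausible, though the documents do not establish it. Finally, a common slope would be learned mainly from treated subjects, since the active arm supplies 8 of the 10 within-arm baseline degrees of freedom.

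All of this stands, and it limits the point to the arm comparison. It does not remove it. The protocol relies on that comparison to interpret the active arm, listings show an imbalance without correcting for it, and the possible loss of precision is small.

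**Conclusion.** The point holds in a limited form. Both Part D MMRMs omit an available baseline, and at 9 vs 3 an appreciable chance imbalance is likely (SD 0.67 baseline SD). For the allocation actually drawn, a fraction (1 - r) of it enters any comparison of the arms with reversed sign, three quarters of that through the placebo mean. The effect is material if r is near 0.5 to 0.7 and small if r is 0.9 or more. These sizes rest on equal variances, a common r and complete data; treatment could change the variance or the correlation in the active arm. The stronger conclusion, that the planned within-group analyses are wrong or biased, is not supported.

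**What to change.** Add to SAP 9.3.1 and 9.6, before database lock, a second MMRM for the arm comparison. Suggested text: *The MMRM will also be fitted with centred baseline ppFEV1 (for sweat chloride, centred baseline sweat chloride) as a continuous fixed effect. From this model, each arm's adjusted mean at the overall baseline mean, and the TC-minus-placebo difference averaged over Days 15 and 29 with its 2-sided 95% CI, will be reported descriptively. Within-group CIs and P values will come from the model without baseline.*

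The last sentence matters because within-group CIs from the adjusted model can under-cover (working, step 6). No P value for the difference is needed, which is consistent with the descriptive intent of protocol 12.3.1.

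The cost is one model term, a few SAP sentences and one degree of freedom. The arm-difference CI would be about 3% to 5% wider if r is 0.9 to 0.95, about 13% narrower at r = 0.5, and unchanged near r = 0.8. The SAP should say that the common slope will be estimated mainly from the active arm.

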### **Part D**

Part D will evaluate the safety, tolerability, PK, PD, and efficacy of VX-121 administered in TC with TEZ/IVA in subjects with CF who are heterozygous for *F508del* and a MF *CFTR* mutation (F/MF genotype).

Efficacy has not been established for a corrector, potentiator, or any corrector/potentiator combination in subjects with F/MF genotypes. Because there is no effective treatment for this

population, a placebo arm will be included as the control treatment to assess whether any observed effects are treatment-related or simply related to the study conditions.

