**9.5.2 Part D**

Information regarding all prior and concomitant medications, including the subject's CF medications, other medications, and herbal and naturopathic remedies administered from 28 days before the Screening Period through the Safety Follow-up Visit, if applicable, will be recorded in each subject's source documents. For subjects who are screened but are not subsequently randomized in the study, details of prior medication will be documented only in the subjects' source documents.

- Subjects must remain on a stable CF medication (and supplement) regimen (other than protocol-specified changes in CFTR modulator regimen) for their CF from 28 days before the Day 1 Visit through the Safety Follow-up Visit. Stable CF medication regimen is defined as the current medication regimen for CF that subjects have been following for at least 28 days before the Day 1 Visit. Subjects must not initiate long-term treatment with new medication from 28 days before the Day 1 Visit through the Safety Follow-up Visit unless discussed and approved by the medical monitor. Guidelines for stable CF medication regimens for CF are as follows:
  - Subjects who are taking daily inhaled tobramycin or other chronically inhaled antibiotics should remain on that regimen throughout the study.
  - Subjects who cycle onto and off an inhaled antibiotic should continue on their prior schedule. The timing of the first dose of study drug on the Day 1 Visit should be synchronized as closely as possible (and not more than  $\pm$  3 days) to the first day in the cycle onto the inhaled antibiotic.
  - Subjects who alternate between 2 different inhaled antibiotics should remain on the same cycling schedule during the study. The timing of the first dose of study drug on the Day 1 Visit should be synchronized as closely as possible (and not more than  $\pm$  3 days) to the first day in the cycle onto 1 of the inhaled antibiotics.
- Subjects may receive doses of prednisone or prednisolone of up to 10 mg/day or equivalent (chronically), or prednisone or prednisolone 60 mg/day for up to 5 days, without prior approval of the medical monitor.

- Information about bronchodilator use during the study will be collected and documented. Subjects who are using a bronchodilator must have their spirometry assessments performed according to the guidelines provided in [Section 11.7.5](#).

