### **12.3.1 General Considerations**

Only descriptive analyses will be performed; no statistical hypothesis testing will be done. Continuous variables will be summarized using the following descriptive summary statistics: the number of subjects (n), mean, SD, SE, median, minimum value, and maximum value. Categorical variables will be summarized using counts and percentages.

All individual subject data for subjects who were randomized or received at least 1 dose of study drug will be presented in individual subject data listings.

For Parts A, B, and C, the **Treatment-emergent (TE) Period** will be from the first dose date of study drug to (1) the Safety Follow-up Visit for subjects who have a Safety Follow-up Visit, or (2) 7 days after the last dose of study drug for subjects who do not have a Safety Follow-up Visit.

For Part D, the **TE Period** will be from first dose date of study drug to 28 days after the last dose date of study drug.

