#### **12.3.3 Efficacy Analysis**

##### **12.3.3.1 Spirometry (Part D Only)**

The following parameters of  $FEV_1$  (L), forced vital capacity (FVC) (L),  $FEV_1/FVC$  (ratio), and forced expiratory flow, midexpiratory phase ( $FEF_{25\%-75\%}$ ) (L/s) will be summarized using descriptive statistics for the FAS.

In addition, a mixed-effects model for repeated measures (MMRM) with change from baseline for percent predicted forced expiratory volume in 1 second (pp $FEV_1$ ) as the dependent variable will be performed for the FAS. The model will include treatment group, visit, and treatment-by-visit interaction as fixed effects. The model will be estimated using restricted maximum likelihood. Denominator degrees of freedom for the *F* test for fixed effects will be estimated using the Kenward-Roger approximation. A compound symmetry covariance structure will be used to model the within-subject errors. Conditional on the fixed effects, missing data due to treatment or study discontinuation will be assumed to be missing at random.

Descriptive analyses of the change from baseline will be performed for VX-121 TC and placebo. Adjusted means and 2-sided 95% CIs of the treatment effect through Day 29 (averaged over Day 15 and 29), with *P* values for all within-group comparisons, will be estimated within MMRM.

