#### **12.4.2 Pharmacodynamic Analysis (Part D Only)**

The sweat chloride assessment will be performed in Part D to evaluate the effect of VX-121 on sweat chloride levels. The analysis of sweat chloride data will be based on the FAS and will be summarized using descriptive statistics.

In addition, the same MMRM model as for ppFEV1 will be used to analyze the change from baseline for sweat chloride. Adjusted means and 2-sided 95% CIs of the treatment effect through Day 29 (averaged over Day 15 and 29), with *P* values for all within-group comparisons, will be estimated within MMRM.

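### Part D requests no TC-minus-placebo estimate for ppFEV1 or sweat chloride: the treatment effect is undefined and P values are within-group only

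*SAP*

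**What the plan says.** SAP 9.3.1 fits an MMRM to change from baseline in ppFEV1 with treatment, visit and treatment-by-visit as fixed effects. It asks for adjusted means and 95% CIs of a treatment effect averaged over Days 15 and 29, with P "values for all within-group comparisons, will be estimated using MMRM". The only further model output is "the adjusted mean and 95% CI of the within-treatment difference at each post-baseline visit through Day 29 for each treatment group", with a P value.

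SAP 9.6 uses the same model for sweat chloride and requests "Adjusted means and 2-sided 95% CIs of the treatment effect through Day 29 (averaged over Day 15 and 29"), again with P values for within-group comparisons.

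The protocol matches. Section 12.3.3.1 states "Descriptive analyses of the change from baseline will be performed for VX-121 TC and placebo" and then gives the same model outputs. Section 12.4.2 repeats them for sweat chloride, with P "values for all within-group comparisons, will be estimated within MMRM".

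Neither document says what the treatment effect is compared with, and neither names a TC-minus-placebo difference, its interval or its P value. On the purpose of the control, protocol 9.3.1 (Part D) says that "a placebo arm will be included as the control treatment to assess whether any observed effects are treatment-related" as opposed to a product of the study conditions. Protocol 12.3.1 adds, in general terms, "Only descriptive analyses will be performed; no statistical hypothesis testing will be done".

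**The concern.** Part D is randomised and placebo-controlled so that drug effect can be told apart from whatever else happens over four weeks in a trial. That is a between-arm question, and the listed outputs give no interval that answers it. If the within-TC estimate is reported as the treatment effect, any change common to both arms is credited to the drug.

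The protocol itself contains one possible source of common change. Under 9.5.2, subjects who cycle inhaled antibiotics have Day 1 aligned, to within 3 days, "to the first day in the cycle onto the inhaled antibiotic". This bears on ppFEV1 only, and only in subjects who cycle; the documents give neither its direction nor its size. The argument does not depend on it, because the stated reason for the placebo arm already allows for effects of study conditions.

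Showing the placebo result beside TC does not repair the gap. With 9 and 3 subjects, the same true change is far more likely to reach P<0.05 on TC than on placebo.

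**Working it through.** **Plan's own figure.** There is none to reproduce: SAP 7.3 and protocol 12.1 state that no sample size calculation was made, and no SD or effect size is given. Twelve subjects at 3:1 give 9 on TC and 3 on placebo, as in protocol Figure 9-1.

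**Set-up.** Let s be the SD of a subject's change averaged over Days 15 and 29 (not in the documents). With complete data, equal variances and the planned compound symmetry, the averaged contrast reduces to a t statistic on one value per subject, with 9 + 3 − 2 = 10 df and t(0.975) = 2.228.

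**Precision.** Half-width = 2.228 × SE.

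| Estimate | SE | 95% half-width |
|---|---|---|
| Within TC | s/√9 = 0.333s | 0.743s |
| Within placebo | s/√3 = 0.577s | 1.286s |
| TC minus placebo | s√(1/9 + 1/3) = 0.667s | 1.485s |

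For assumed s of 4, 6 or 8 ppFEV1 points, the half-width is 3.0, 4.5 or 5.9 points within TC and 5.9, 8.9 or 11.9 points for the difference. For sweat chloride, assumed s of 10 or 15 mmol/L gives 7.4 or 11.1 within TC and 14.9 or 22.3 for the difference.

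**Effect of a common drift when the drug does nothing.** Let both arms shift by the same amount d (in units of s; assumed values). The within-group tests follow a noncentral t on 10 df with noncentrality 3d for TC and √3 × d for placebo. The joint pattern was simulated with the shared pooled variance, 2,000,000 trials per drift.

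| Drift d | TC P<0.05 | Placebo P<0.05 | TC P<0.05 and placebo not | TC minus placebo P<0.05 |
|---|---|---|---|---|
| 0.25 | 10% | 7% | 9% | 5% |
| 0.5 | 27% | 12% | 23% | 5% |
| 0.75 | 53% | 22% | 39% | 5% |
| 1.0 | 77% | 35% | 48% | 5% |

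The arm sizes produce the asymmetry. At d = 0.5, both arms reach P<0.05 in 27.4 − 22.7 = 4.7% of trials, so placebo alone does so in 12.3 − 4.7 = 7.6%, against 22.7% for TC alone, although the true change is identical.

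**What the added contrast can detect.** At two-sided 5%, power is 27% for a true difference of 1s, 53% for 1.5s, 77% for 2s and 92% for 2.5s. The difference detectable with 80% power is 2.07s.

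**The case against.** Five points can be made for the plan as written.

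- *The undefined term may already mean TC minus placebo, with only the P values limited to within-group comparisons.* That reading is possible. But every comparison named in the same sentence is within-group, and SAP 9.3.1 then adds only within-treatment differences. Two programmers could produce different tables, so the term needs a definition either way.
- *No decision rule is attached.* True: there is no alpha or success criterion, and the endpoint is described as preliminary. The percentages above describe a reading that the plan invites but does not prescribe.
- *The drifts are hypothetical, and the protocol limits drift* through stable disease and medication before Day 1, a stable regimen through follow-up, and pre-bronchodilator spirometry at a consistent time of day. This stands. Those controls reduce drift without excluding it, and no mechanism is offered for sweat chloride.
- *Little information is lost.* With complete data, a reader can subtract the two adjusted means and rebuild the SE as √(0.333² + 0.577²)s = 0.667s. This also stands: the model can deliver the comparison. It is a reason to print the result, since the planned output draws attention to the narrower within-TC interval.
- *The tension with the no-testing statement is small.* The protocol synopsis, like SAP 9.4, attaches that statement to safety data. Protocol 12.3.1 remains generally worded, so a minor inconsistency is left.

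**Conclusion.** The concern holds for both endpoints and in both documents. The treatment effect has no stated comparator, no TC-minus-placebo estimate or interval is requested, and the only planned P values cannot serve the purpose given for the placebo arm. Under the assumed common drifts of 0.25s to 1.0s with no drug effect, within-TC significance appears in 10% to 77% of trials, and TC significance without placebo significance in 9% to 48%.

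These rates rest on assumed drifts, complete data, equal variances and compound symmetry; s and the drifts are not in the documents, and nothing shows that drift will occur. The textual finding needs none of these assumptions. The issue concerns what Part D can conclude on efficacy and pharmacodynamics, which are secondary endpoints. It should be fixed, but it does not threaten the primary safety objective.

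**What to change.** In SAP 9.3.1 and 9.6, and in protocol 12.3.3.1 and 12.4.2, define the treatment effect as the TC-minus-placebo difference in adjusted means from the MMRM already specified. Report it with a 95% CI at Day 15, at Day 29 and averaged over both, for ppFEV1 and sweat chloride, and state that it is an estimate and not a formal test. Keep the within-group means and intervals as supportive results and label their P values descriptive, which also removes the tension with protocol 12.3.1.

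The cost is a few sentences and one added treatment contrast in each model (by visit and averaged), with no new data. The drawback should be stated with the result: the between-group interval is twice as wide as the within-TC one (1.485s/0.743s = 2.0) and rests on 3 placebo subjects.
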